9.7 Interim Monitoring and Analyses

Formal interim analyses of the accumulating data will be performed at regular intervals (at least annually) for review by an Independent Data Monitoring and Safety Committee (IDSMC). These analyses will be performed at the Clinical Trials Research Centre. The IDSMC will be asked to give advice on whether the accumulated data from the trial, together with results from other relevant trials, justifies continuing recruitment of further patients or further follow-up. A decision to discontinue recruitment, in all patients or in selected subgroups will be made only if the result is likely to convince a broad range of clinicians including participants in the trial and the general clinical community. If a decision is made to continue, the IDSMC will advise on the frequency of future reviews of the data on the basis of accrual and event rates. The IDSMC will make recommendations to the Trial Steering Committee (TSC, see section 16) as to the continuation of the trial.

After the primary outcome data are available from 25 patients (o-SCORAD index at 12 weeks) the standard deviation of the 25 scores, and the 95% confidence limits for this estimate, will be calculated without unblinding allocation. If the 95% confidence limits of the estimate of the SD of the o-SCORAD index at 12 weeks overlap 10 the trial will continue unchanged. If the upper 95% confidence limit of the estimate of the SD of the o-SCORAD index at 12 weeks is less than 10 the trial will continue unchanged but the TSC will be informed that the trial power is greater than planned. If the lower 95% confidence limit of the estimate of the SD is greater than 10 the study is underpowered. EME will decide whether to invite an extension or close the study.

A comprehensive statistical analysis plan will be developed before any formal statistical analyses are carried out.

The primary analysis will use the principle of intention to treat based on all the randomised participants, as far as is practically possible. If consent for treatment is withdrawn but the participant is happy to remain in the study for follow-up, they will be followed up until completion. However if they decide to withdraw consent completely then the reasons for withdrawal of consent will be collected (if possible) and reported for both groups.

The analysis of change in o-SCORAD from baseline to 12 weeks will use the method of analysis of covariance and the covariates that will be used in the model will be treatment group and the baseline measurement

Analysis of time to first significant flare after treatment cessation will be summarised by Kaplan-Meier curves for each treatment group and compared overall using the log rank test and survival regression methods. The time to first significant flare after treatment cessation will be measured from randomisation.

For the secondary outcomes, continuous data will be reported as difference in means and will be analysed using ANCOVA where appropriate and binary data will be reported in terms of relative risk with appropriate 95% confidence intervals.

Missing data will be monitored and strategies developed to minimise its occurrence. Missing data will be handled by considering the robustness of the complete case analysis to sensitivity analyses using various imputation assumptions; however these will be informed by data collected on the reasons for missing data.

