6.5.2 Discontinuation from Trial Intervention

Patients will be discontinued from treatment for any of the following reasons:

- a. Parent/ legal representative (or, where applicable, the patient) withdraws consent.
- b. Unacceptable toxicity based on investigator's judgement
- c. Development of illness preventing further treatment.
- d. Any change in the patient's condition that justifies the discontinuation of treatment in the clinician's opinion.
- e. Patient cannot be monitored as per protocol

If a patient wishes to discontinue from trial treatment, centres should nevertheless explain the importance of remaining on trial follow-up, or failing this, of allowing routine follow-up

data to be used for trial purposes. Generally, follow-up will continue unless the patient explicitly also withdraws consent for follow-up (see section 6.5.3).

Should a trial participant be administered one of the trial treatments (ciclosporin or methotrexate) as part of routine clinical care following cessation of their trial treatment then safety reporting procedures should be followed as described in section 10.

Data collected from participants who discontinue from trial treatment prior to week 36, will differ from those still on trial treatment as the collection of trial data and samples will be reduced. If the participant is administered one of the trial treatments (ciclosporin or methotrexate) as part of routine clinical care following cessation of their trial treatment (prior to week 36), information relating to drug monitoring should not be recorded on the CRFs (except for on the concomitant medication form).

The following data **should only** be collected for participants who have been discontinued from trial treatment between randomisation and week 36:

Table 1. Schedule of study procedures (patients discontinued from trial treatment)

	Week 1	Week 2	Week 4	Week 8	Week 12	Week 20	Week 28	Week 36	Week 48	Week 60	Unscheduled visit
Procedures	Visit 1	Visit 2	Visit 3	Visit 4	Visit 5	Visit 6	Visit 7	Visit 8	Visit 9	Visit 10	
Concomitant drugs	x	x	x	x	x	x	x	x	X	x	Х
o-SCORAD)			x	x	х	x	х	х	X	x	X (if required)
EASI, IGA			X	X	X	X	X	X	X	X	X (if required)
POEM (patient assessed) (Post 36 week patient diary)			X	X	X	X	X	X	х	X	
Parent and child QoL (CDLQI/IDQOL & DFI)					x			x	X	х	
Child HRQL (CHU-9D)					x			x	x	x	
Resource Use (post 36 week patient diary)			X	X	Х	X	х	X	X	X	
Adverse events (AE & SAE)	Collec	ted unti	4 week	s after t	trial trea	tment s	topped				

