8 ASSESSMENTS AND PROCEDURES

8.1 Schedule for assessments during the treatment and the follow-up phase

The total duration of the study is for 60 weeks (following randomisation). Patients will receive IMP for 36 weeks and followed up for 60 weeks post randomisation. The below interventions will take place according to the study visit schedule table at the stated time points. However, the following visit windows are allowed: 2 days +/- at week 1 and 2, 1 week +/- at week 4, and then 2 weeks +/- thereafter.

Table 9: Schedule of study procedures

		Week 0	Week 1 (MTX arm only)	Week 2	Week 4	Week 8	Week 12	Week 20	Week 28	Week 36	Week 48	Week 60	Unschedule d visit
Procedures	Screening Visit	Baseline/ Randomis ation	Visit 1	Visit 2	Visit 3	Visit 4	Visit 5	Visit 6	Visit 7	Visit 8	Visit 9	Visit 10	
Informed consent	х												
Inclusion/exclusion criteria	х	х											
Medical history	х												
Concomitant drugs	х	х	х	x	x	х	х	х	x	х	х	x	х
Demographics	х												
Physical exam (including mouth/throat examination and chest auscultation)		x	x	x	x	x	x	x	x	x	x	х	
o-SCORAD)	х	х			x	х	x	х	x	х	х	х	x ^h
EASI, IGA		x			x	х	х	x	x	х	х	х	x ^h
POEM (patient assessed) Parent and child QoL		х			х	х	х	х	x	х	х		
(CDLQI/IDQOL & DFI)		х					х			х	х	х	
Child HRQL (CHU-9D)		х					х			х	х	х	
Resource Use (patient diary)		х			x	х	x	х	x	х	х	х	
Height & weight		х	х	х	x	х	х	х	x	х		х	
Height	х												() '(
Blood pressure		х		х	x	х	х	х	x	х		х	x (only if required)
Adverse events (AE & SAE)			x	x	х	х	х	х	x	х			x
Safety bloods ^b	Х ^с		х	x	x c	х	х	х	x	х		x	x (only if required)
Chest X-Ray d	х												
Pregnancy test (beta-HCG) Confirmation of appropriate	х	х											
contraception use, where applicable	x	x	x	x	x	x	x	x	x	x	x	x	x
Urine sample collection (NAG)		х		x			x			х		х	
Randomisation		x											
Study drug dispensing (as needed at each visit)		х			x	х	х	х	x				
MTX metabolite level (blood)				x		х	x			х			
CyA trough level (blood) e				х		х	х			х			_
Cystatin C level (blood)		x		х		х	х			х		х	
Creatinine level (blood)		х		x		х	х			х		х	
Tape stripping for cutaneous metabolic work f		х					х			х		х	
Collection of blood for mechanistic studies ^g		х					x			х		х	
Collection of blood/saliva for FLG genotyping i		х											

8.1.1 Assessments:

- a. Children will be assessed by trained blinded assessors at 0, 4, 8, 12, 20, 28, 36, 48 and 60 weeks (o-SCORAD, EASI, & IGA). POEM (included in the patient diary) will be completed by the patient/parent at home.

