9.6 Sample Size

For the first primary outcome (o-SCORAD), the change from baseline to 12 weeks will be calculated for each participant. The study aims to detect a difference of 8 o-SCORAD points, assuming a standard deviation (SD) of 10 (based on the only other paediatric RCT with systemic immunosuppressive medication in children (7), which saw a SD of 6.3 (MTX arm) vs 8.9 (CyA arm) at 12 weeks) a sample size of 41 per group, increasing to 49 per group to allow for an estimated 18% loss to follow up, will be required to provide 90% power using a t-test with a 0.025 two-sided significance level. Our assumption of 8 Units in the o-SCORAD index representing the minimal clinically important difference between treatments is based on calculations from three other RCTs with immuno-suppressive medication in children and adults with severe atopic eczema (33).

The co-primary outcome of this trial is time to first significant flare after treatment cessation (return to baseline o-SCORAD (or worse) or re-starting systemic treatment), as this may be an important factor influencing potential change in prescribing behaviour. The number of patients on CyA burst treatment who went into remission after the first three months of treatment in the study by Harper et al was three out of 21, indicating that 86% of patients reflared. Assuming a similar flare risk in our CyA group, a sample size of 43 in each group (51 in each group with estimated loss to follow up of 18%) will have 80% power to detect a reduction in re-flare of 30% (from 86% to 56%) using a two-sided test with a 0.025 significance level.

Randomising a total of 102 participants, 51 into each of the study arms, satisfies both sample size calculations.

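### The reference analysis for the week-12 o-SCORAD co-primary is a complete-case ANCOVA, so children with week-4 or week-8 scores but no week-12 score add nothing to the primary estimate

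*Protocol*

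**What the plan says.** Section 9.7 of the protocol names the model for the first co-primary, an ANCOVA of the change in o-SCORAD from baseline to week 12, and fixes its terms: "the covariates that will be used in the model will be treatment group and the baseline measurement". The same section ranks the analyses when data are missing: "Missing data will be handled by considering the robustness of the complete case analysis to sensitivity analyses using various imputation assumptions", adding "however these will be informed by data collected on the reasons for missing data". The analysis set is described as follows: "The primary analysis will use the principle of intention to treat based on all the randomised participants, as far as is practically possible".

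Section 8.1.1 gives the assessment times for o-SCORAD, EASI and IGA: "Children will be assessed by trained blinded assessors at 0, 4, 8, 12, 20, 28, 36, 48 and 60 weeks". Table 1 in section 6.5.2 keeps o-SCORAD at weeks 4, 8 and 12 for children who have stopped trial treatment, and the section says of them: "Generally, follow-up will continue unless the patient explicitly also withdraws consent for follow-up".

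Section 9.6 sets the target: "The study aims to detect a difference of 8 o-SCORAD points, assuming a standard deviation (SD) of 10". It requires 41 per group for 90% power at two-sided 0.025, raises this to 49 for an estimated 18% loss, and randomises 51 per group.

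**The concern.** The protocol has already chosen which number is the primary result. An ANCOVA with only treatment and baseline has no place for the week-4 and week-8 scores. A child seen by the blinded assessor at both visits who then misses week 12 is left out of the primary estimate altogether. An imputation that used those scores would appear only as a sensitivity analysis.

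Complete-case ANCOVA is unbiased if, given arm and baseline, missing week 12 is unrelated to the week-12 outcome. That is doubtful if leaving depends on how the child is doing at weeks 4 and 8. Section 6.4.2 says families know the allocation and that the drugs have different side-effect profiles. Section 2.1 describes a slow onset for methotrexate. Dropout linked to early response, and at different rates by arm, is therefore conceivable. The stake is a biased treatment difference in a co-primary outcome, when scores that could correct it are already being collected.

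**Working it through.** **1. The plan's own figure.** With difference 8, SD 10 and two-sided alpha 0.025, the noncentral t gives power 89.9% at 40 per group and 90.7% at 41, so 41 is reproduced. The stated 49 is 41 × 1.18 = 48.4, rounded up.

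**2. How many children are affected.** At 18% loss, 0.18 × 51 = 9.2 per arm, or about 18 of 102, have no week-12 score. That leaves 51 × 0.82 = 41.8 per arm, still above 41, so planned power is intact. The question is bias.

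**3. Size of the bias in general.** Let p be the proportion missing in an arm. Let d be the mean week-12 score of missing children minus that of observed children, given baseline. The complete-case arm mean is off by about p × d, so

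bias in the difference ≈ p₁d₁ − p₀d₀.

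- Equal p and equal d: 0.
- p = 0.18 in both arms, d differing by 5 points: 0.18 × 5 = 0.9.
- p = 0.18 in both arms, d differing by 10 points: 0.18 × 10 = 1.8.
- d = 5 in both arms, p = 0.10 versus 0.26: 0.16 × 5 = 0.8. The sign reverses if the higher rate is in the other arm.

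**4. Simulation.** The protocol gives no correlations and no dropout pattern, so these inputs are assumptions: true difference 8; SD 10 at every visit; correlations between visits of 0.4 to 0.7; log-odds of missing week 12 of ±1 per SD of the week-8 score. Complete-case ANCOVA is compared with an analysis that fills in week 12 from arm, baseline, week 4 and week 8.

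| Dropout pattern | Complete-case estimate | Using weeks 4 and 8 |
|---|---|---|
| Unrelated to week 8, 18% per arm | 8.0 | 8.0 |
| Same dependence, 18% per arm | 8.0 | 8.0 |
| One arm only, 18% per arm | 8.8 | 8.0 |
| Opposite directions, 18% per arm | 9.7 | 8.0 |

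The third row implies d of about 0.83/0.18 = 4.6 in the affected arm. Putting this into the formula:

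- same direction, 10% versus 26%: 0.16 × 4.6 = 0.7;
- one arm only, with 26% missing there: 0.26 × 4.6 = 1.2;
- opposite directions at 18%: 2 × 0.18 × 4.6 = 1.7.

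Simulations at 51 per arm with correlations in similar ranges agree: 0.7 to 0.8, 1.2 to 1.3, and 1.8 to 2.0. With weeks 4 and 8 used, the error stays within 0.1.

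**5. Less loss at week 12.** At an assumed 9% missing, the error was about 0.3 (same direction, 6% versus 12%), 0.5 (one arm only) and 0.9 (opposite directions).

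**6. Precision.** Under random dropout the standard error falls from 2.03 to 1.93, about 5% (1 − 1.93/2.03).

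**The case against.** Much of the case for leaving the plan alone is sound.

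- **Intention to treat.** A reader might infer that complete case contradicts the sentence on all randomised participants. It does not, because that sentence carries its own qualifier on what is practical. The tension is that the week-4 and week-8 scores are scheduled, so using them is practical.
- **Size.** A reader might infer a bias of 2 to 3 points. Reaching about 2.8 took opposite dependence in the two arms and a slope of 2 log-odds per SD, and nothing in the protocol supports that pattern. The plausible story, poor early responders leaving both arms at unequal rates, gives under half a standard error (about 2.0).
- **The 18%.** Section 9.6 applies the same allowance to the flare outcome, which is followed to week 60. Loss by week 12 may well be lower, and the bias shrinks with it.
- **Routes to missingness.** Children who stop treatment stay in follow-up and keep their o-SCORAD visits, and section 7.7.1 permits rescue oral corticosteroids. A poor response need not remove the week-12 score.
- **Sensitivity analyses.** They are planned in advance and informed by recorded reasons, and a SAP not shown may specify that they use weeks 4 and 8. Even so, they would leave the primary number as it is.
- **The alternative is not perfect.** A repeated-measures model is also biased if dropout depends on the unseen week-12 score, and children lost before week 4 remain outside it.

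These points limit the size and tone of the concern. They do not supply a reason to leave the interim scores out of the primary analysis.

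**Conclusion.** The concern holds in a limited form. The protocol makes complete-case ANCOVA the reference analysis for the 12-week co-primary and leaves collected, blinded interim scores unused. The resulting bias is conditional. It is nil under random dropout, or when dependence on early response and missing rates are the same in both arms. It is about 0.8 points when poor early responders leave both arms at 10% versus 26%. It is at most about 2 points, a quarter of the 8-point target (2/8), in the least favourable pattern examined at 18% missing and a slope of 1 log-odds per SD. Correlations, slopes and rates by arm are assumptions. Lower week-12 loss gives smaller figures and steeper slopes give larger ones. The documents support neither a contradiction of the intention-to-treat principle nor a loss of planned power.

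**What to change.** Make the primary analysis of the first co-primary a likelihood-based repeated-measures model on o-SCORAD at weeks 4, 8 and 12, with treatment-by-visit and baseline-by-visit terms and unstructured covariance. Include every randomised child with at least one post-baseline score and report the week-12 treatment contrast. An acceptable alternative is multiple imputation by arm using baseline, week 4 and week 8, followed by the ANCOVA already named. Keep complete-case ANCOVA as a sensitivity analysis, together with imputations that assume data missing not at random and are guided by the recorded reasons.

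The cost is a change of wording in section 9.7 and in the SAP, and slightly more modelling. The week-12 contrast is unchanged and no new data are required. The new primary analysis assumes data missing at random given baseline and the earlier scores. That is ordinarily a weaker requirement than complete case needs, but it is still untestable.

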10 PHARMACOVIGILANCE

10.1 Terms and Definitions

The Medicines for Human Use (Clinical Trials) Regulations 2004 (SI 2004/1031) definitions:

Adverse Event (AE)

Any untoward medical occurrence in a subject to whom a medicinal product has been administered, including occurrences which are not necessarily caused by or related to that product.

Adverse Reaction (AR)

Any untoward and unintended response in a subject to an investigational medicinal product which is related to any dose administered to that subject.

Unexpected Adverse Reaction (UAR)

An adverse reaction the nature and severity of which is not consistent with the information about the medicinal product in question set out in:

In the case of a product with a marketing authorization, in the summary of product characteristics for that product

In the case of any other investigational medicinal product, in the investigator's brochure relating to the trial in question.

Serious Adverse Event (SAE), Serious Adverse Reaction (SAR) or Suspected Unexpected Serious Adverse Reaction (SUSAR)

Any adverse event, adverse reaction or unexpected adverse reaction, respectively, that:

- results in death
- is life-threatening* (subject at immediate risk of death)
- requires in-patient hospitalisation or prolongation of existing hospitalisation**
- · results in persistent or significant disability or incapacity, or
- · consists of a congenital anomaly or birth defect
- Other important medical events***

*'life-threatening' in the definition of 'serious' refers to an event in which the patient was at risk of death at the time of the event; it does not refer to an event which hypothetically might have caused death if it were more severe.

**Hospitalisation is defined as an inpatient admission, regardless of length of stay, even if the hospitalisation is a precautionary measure for continued observation. Hospitalisations for a pre-existing condition, including elective procedures that have not worsened, do not constitute an SAE.

***Other important medical events that may not result in death, be life-threatening, or require hospitalisation may be considered a serious adverse event/experience when, based upon appropriate medical judgment, they may jeopardise the subject and may require medical or surgical intervention to prevent one of the outcomes listed in this definition

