2 BACKGROUND INFORMATION

2.1 Introduction

Background

Atopic eczema is a chronic, pruritic inflammatory skin disease and affects around 20% of UK children, 16% of whom have moderate-severe disease(1). It comes at a high cost, both for the individual patient and their family as well as society at large (~£500mio per year in the UK alone, 21st cause of non-fatal burden of all diseases) (2, 3). Patients with severe atopic eczema suffer significant sleep disturbance, show poor school attendance and are often socially withdrawn and are significantly more likely to suffer of attention-deficit hyperactivity disorder. There is also a clear link with anxiety and depression. Skin infections, in particular with Staphylococcus aureus but also herpes simplex, leading to hospital admissions are another typical feature of poorly controlled eczema(4). Although most cases of atopic eczema are adequately controlled with emollients and topical treatments and/or UV therapy, around 2% of children require oral immuno-suppressive treatment to induce and maintain disease control (5). The European TREAT Survey

The currently available treatment options for severe atopic eczema in children are very limited, and there is concern about their potential short and long-term side effects (5). We consequently conducted the TREatment of severe Atopic eczema in children Taskforce (TREAT) survey among 765 consultant dermatologists and paediatricians from 8 European countries. This showed that 43% of European physicians who look after children with severe atopic eczema use Cyclosporine A (CyA) as their first choice systemic immuno-suppressive agent (6). 31% use oral corticosteroids (CS) and 22% azathioprine (AZA) as 1st choice. However, the situation in the UK is a little different, where 39% use AZA first line compared to 35% for CvA and 19% for CS. Although MTX was only the 3rd most commonly used systemic treatment for severe atopic eczema in the TREAT survey, there has been a lot of interest in its use since two recent randomised controlled trials (RCTs) suggested no significant difference in efficacy between MTX and AZA (adults with severe atopic eczema, n=42) and MTX and CyA (children, n=40) (7, 8). However, both studies were statistically underpowered (9). In addition, the paediatric trial lacked an intention-to-treat analysis and lower than conventional drug doses were used (CvA 2mg/kg/d; MTX 7.5mg/week, not adjusted by weight).

Cyclosporine A

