10.2 Notes on Adverse Event Inclusions and Exclusions

10.2.1 Include

- An exacerbation of a pre-existing illness
- An increase in frequency or intensity of a pre-existing episodic event/condition
- A condition (even though it may have been present prior to the start of the trial) detected after trial drug administration
- Continuous persistent disease or symptoms present at baseline that worsens following the administration of the study/trial treatment
- Laboratory abnormalities that require clinical intervention or further investigation (unless they are associated with an already reported clinical event).
- Abnormalities in physiological testing or physical examination that require further investigation or clinical intervention
- Injury or accidents

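### A misplaced qualifier in the hospitalisation note of section 10.1 lets admissions for a worsened pre-existing condition escape the hospitalisation criterion for an SAE

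*Protocol*

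**What the plan says.** Protocol section 10.1 lists the criteria that make an event serious. One is that the event "requires in-patient hospitalisation or prolongation of existing hospitalisation". A footnote (marked **) defines the term broadly: "Hospitalisation is defined as an inpatient admission, regardless of length of stay, even if the hospitalisation is a precautionary measure for continued observation". The next sentence of the same footnote takes something away again: "Hospitalisations for a pre-existing condition, including elective procedures that have not worsened, do not constitute an SAE".

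Section 10.2 deals with the prior question of what counts as an adverse event at all. Section 10.2.1 includes "An exacerbation of a pre-existing illness" and also "Continuous persistent disease or symptoms present at baseline that worsens following the administration of the study/trial treatment". Section 10.2.2 leaves out pre-existing conditions only when they do not worsen. It leaves out the disease under treatment unless it is more severe than expected for that patient.

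The classification decides the reporting route. Under section 10.8 an SAE goes to the coordinating centre within 24 hours, and other adverse events go on the regular follow-up reports. Section 10.9 has the Chief Investigator evaluate the SAEs received for seriousness, expectedness and causality.

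**The concern.** The footnote is an operative rule: site staff apply it when deciding whether an admission needs an SAE form. Its only limiting words sit next to the elective procedures, to which they cannot sensibly apply. The pre-existing condition, to which they could apply, is left without a limit.

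This matters in this trial for three reasons.

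- Every child enters with severe atopic eczema, and section 7.7.1 expressly allows maintenance treatment for asthma. Admissions for a condition that existed before entry are foreseeable.
- Section 7.3.3 makes new or worsening unexplained dyspnoea or cough a monitoring parameter for methotrexate. A respiratory admission in a child with known asthma is therefore one where prompt review of causality is useful, and the footnote invites classing it as pre-existing.
- Section 6.4.2 says that local investigators know the allocation, and section 10.9.1 uses SAE reporting rates to monitor sites. An ambiguous seriousness rule leaves room for differences between arms or sites that reflect how the sentence was read and not what happened to the children.

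**Working it through.** The protocol gives no figure on this point, so the check is of the text.

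1. **Grammar of the footnote.** The verb is plural (*have* not worsened). It agrees with the plural *procedures*, which it directly follows, and not with the singular *condition*. As printed, the exclusion has no limit on the state of the pre-existing condition.

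2. **Sense of the footnote.** A procedure cannot worsen, so on the printed attachment the qualifier does no work. This points to a misplaced phrase.

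3. **Comparison with 10.2.**

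| Section | Question it settles | What worsening attaches to |
|---|---|---|
| 10.1, footnote ** | Is the admission serious? | The elective procedures |
| 10.2.1 | Is it an adverse event? | The pre-existing illness or baseline disease |
| 10.2.2 | Is it left out as an adverse event? | The pre-existing condition; the treated disease has its own threshold |

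   The adverse event lists treat worsening of the condition as decisive. The seriousness footnote, as worded, does not. Because 10.2 answers a different question, it shows intent but does not formally amend 10.1.

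4. **Example: a child with known asthma is admitted because the asthma has worsened.**
   - Under 10.2.1 this is an adverse event.
   - Under the hospitalisation criterion it would be serious.
   - Under the footnote read literally, that criterion is switched off.
   - The life-threatening criterion requires a risk of death at the time of the event, which an ordinary admission may not involve.
   - The important-medical-event criterion is discretionary: such events "may be considered a serious adverse event/experience when, based upon appropriate medical judgment, they may jeopardise the subject". An investigator may use it but need not.
   - A site reading the sentence literally can therefore file the event as non-serious. A site reading the evident intent files an SAE.

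5. **What changes for that admission.** Filed as non-serious, it still goes on an Adverse Event Form (10.7.1), and the investigator still assigns causality (10.4). It misses the 24-hour report (10.8) and the Chief Investigator's SAE evaluation (10.9). While it stays classed as non-serious it does not meet the SUSAR definition in 10.5.

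6. **Example: eczema.** A flare within what is expected for the patient is not an adverse event under 10.2.2, so it cannot be an SAE however the footnote is worded. The footnote matters only for an eczema admission above that threshold.

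7. **Size.** The protocol states no admission rate for eczema, asthma or any other pre-existing condition. With 102 participants, each 1% admitted corresponds to 0.01 × 102 = 1.02, about one child. The rate itself is unknown, so no count follows.

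**The case against.** The strongest reply is that no experienced site would apply the literal reading. It leaves the qualifier meaningless, and 10.2.2 shows that the authors meant worsening to apply to the condition. On this view the sentence is a drafting slip with little practical effect. It is indeed very probably a slip. But expedited reporting should not depend on each site reconstructing the intent, and 10.2 does not settle seriousness.

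A second reply is that 10.1 and 10.2.1 do not contradict each other, because an event can be an adverse event without being serious. That is correct. The sections fit badly together without being in formal conflict.

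Several stronger conclusions are tempting, and the documents do not support them.

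- *Such admissions can never be SAEs or SUSARs.* Only the hospitalisation route is closed. Death, life-threatening events, disability, congenital anomaly and other important medical events remain available.
- *The events are lost to the safety data.* An admission that is an adverse event under 10.2 is still recorded, and section 8.3 has the IDSMC monitor adverse events.
- *Admissions for infected eczema are exempted.* Section 2.1 does say: "Skin infections, in particular with Staphylococcus aureus but also herpes simplex, leading to hospital admissions are another typical feature of poorly controlled eczema". But a new infection during treatment is not plainly a pre-existing condition even on the literal reading, and section 2.1 describes poorly controlled eczema in general.
- *These admissions make up a large share of hospitalisation SAEs.* Nothing in the documents gives a rate or a share.

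**Conclusion.** The point holds as a wording defect in a safety-reporting rule. Read literally, the footnote in 10.1 exempts an admission for a worsened pre-existing condition from the hospitalisation criterion, which does not fit 10.2.1 and 10.2.2.

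The consequence is bounded. For an admission that meets no other seriousness criterion, the 24-hour report and the Chief Investigator's SAE review can be missed, and classification can differ between sites. This rests on the assumption that at least some sites apply the sentence as printed; the documents do not show whether any have. The number of admissions affected cannot be derived. The co-primary analyses are not touched. A correction is worthwhile because the rule governs expedited safety reporting in children on immunosuppressants and is easy to put right.

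**What to change.** Make three changes.

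1. Reword the footnote in 10.1 so that the qualifier belongs to the condition, for example: *Hospitalisation for a pre-existing condition that has not worsened, including for a planned elective procedure, does not constitute an SAE.*
2. Add that admission for a worsened pre-existing condition that is an adverse event under 10.2 meets the hospitalisation criterion. For atopic eczema, make this subject to the severity threshold in 10.2.2. A blanket statement that every admission for worsening eczema is an SAE would contradict that section.
3. Ask sites to recheck admissions already logged against the corrected wording.

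The cost is a short amendment to section 10.1, a note to sites, and possibly a few more SAE forms.
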